## Section 8.3.1 Time period for detecting and recording adverse events, serious adverse events and pregnancies

*For Epoch 002, this includes the assessment of COVID-19 cases in accordance with the WHO definition. Cases should be categorised as AEs (unsolicited or AEs leading to withdrawal) or SAEs (refer to Section 8.1 for safety definitions), and routine procedures for recording, evaluation, follow-up, and reporting of AEs, and SAEs should be followed in accordance with the time period set out in Table 16.*

| Event  | Visit 1 | 6 d post | 29 d post | Visit 3 | 6 d post | 29 d post | Visit 5 | 6 d post | 29 d post | Visit 7 | 6 d post | 29 d post | Study conclusion |
|--|---------|----------|-----------|---------|----------|-----------|---------|----------|-----------|---------|----------|-----------|------------------|
|  | Dose 1  | Dose 1   | Dose 1    | Dose 2  | Dose 2   | Dose 2    | Dose 3  | Dose 3   | Dose 3    | Dose 4  | Dose 4   | Dose 4    |                  |
| Timepoint  | Day 1   | Day 7    | Day 30    | Day 61  | Day 67   | Day 90    | Day 181 | Day 187  | Day 210   | Day 361 | Day 367  | Day 390   | Day 721          |
| AEs/SAEs leading to withdrawal from the study**                      |         |          |           |         |          |           |         |          |           |         |          |           |                  |
| SAEs **  |         |          |           |         |          |           |         |          |           |         |          |           |                  |
| Intercurrent medical conditions leading to exclusion per protocol ** |         |          |           |         |          |           |         |          |           |         |          |           |                  |

**CONFIDENTIAL**

207759 (NTHI MCAT-008)  
Protocol Amendment 3 Final

***\*\* During Epoch 002, if a diagnosis of COVID-19 is made in accordance with the current WHO case definition, cases should be reported as (S)AEs leading to withdrawal) or SAEs (refer to Section 8.1 for safety definitions), and routine procedures for recording, evaluation, follow-up, and reporting of AEs, and SAEs should be followed in accordance with the defined time period***

**Section 10.5.3 Per-protocol set for analysis of immunogenicity**

***Impact on the per protocol set for immunogenicity will be determined on a case by case basis.***

**CONFIDENTIAL**

207759 (NTHI MCAT-008)

Statistical Analysis Plan Amendment 1 Final

**CONFIDENTIAL**

207759 (NTHI MCAT-008)

Statistical Analysis Plan Amendment 1 Final

**CONFIDENTIAL**

207759 (NTHI MCAT-008)

Statistical Analysis Plan Amendment 1 Final

**LIST OF FIGURES**

	PAGE
Figure 1      Study design overview .....	8

**CONFIDENTIAL**207759 (NTHI MCAT-008)  
Statistical Analysis Plan Amendment 1 Final**LIST OF ABBREVIATIONS**

AE	Adverse event
AECOPD	Acute Exacerbation of Chronic Obstructive Pulmonary Disease
AESI	Adverse Events of Special Interest
ANCOVA	Analysis of Covariance
ANOVA	Analysis of Variance
CI	Confidence Interval
COPD	Chronic Obstructive Pulmonary Disease
CTRS	Clinical Trial Registry Summary
eCRF	electronic Case Report Form
Eli Type	Internal GSK database code for type of elimination code
ELISA	Enzyme-linked immunosorbent assay
ES	Exposed Set
EU/ml	ELISA unit per millilitre
FAS	Full Analysis Set
GMC	Geometric mean antibody concentration
GMT	Geometric mean antibody titer
GSK	GlaxoSmithKline
IU/ml	International units per milliliter
LL	Lower Limit of the confidence interval
MedDRA	Medical Dictionary for Regulatory Activities
N.A.	Not Applicable
PCD	Primary Completion Date
PD	Protocol Deviation
PPS	Per Protocol Set

**CONFIDENTIAL**207759 (NTHI MCAT-008)  
Statistical Analysis Plan Amendment 1 Final

[figure not shown]
SAE	Serious adverse event
SAP	Statistical Analysis Plan
SBIR	GSK Biological's Internet Randomization System
SD	Standard Deviation
SHS	Study Headline Summary
SR	Study Report
TFL	Tables Figures and Listings
TOC	Table of Content
UL	Upper Limit of the confidence interval
WBR	Web-based Randomization

**CONFIDENTIAL**207759 (NTHI MCAT-008)  
Statistical Analysis Plan Amendment 1 Final

## 1. DOCUMENT HISTORY

Date	Description	Protocol Version
05-MAR-2018	First version	Final – 28-JULY-2017 - v2.0
09-DEC-2019	Amendment 1: to align with protocol amendment 2 and define safety sets	Amendment 2 - 24-JULY-2019 – v2.0

## 2. STUDY DESIGN

**Figure 1 Study design overview**

**Experimental design:** Phase II, observer-blind, randomised, multi-centric study with two parallel groups.

**Duration of the study:** for each subject enrolled, the study will last approximately 2 years from Visit 1 (enrolment visit):

- Epoch 001 : Primary (Vaccination phase) starting at Visit 1 (Day 1) and ending at Visit 9 (Day 541).
- Epoch 002 : Long-term follow-up starting after Visit 9 (Day 541) and ending at Visit 10 (Day 721).

Primary Completion Date (PCD): Visit 9 (Day 541).

Refer to the Glossary of terms of the protocol for the definition of PCD.

**End of Study (EoS):** Last testing results released of samples collected at Visit 10 (Day 721).

Refer to the Glossary of terms of the protocol for the definition of EoS.

**CONFIDENTIAL**207759 (NTHI-MCAT-008)  
Statistical Analysis Plan Amendment 1 Final

Study groups:

- **Schedule 1** : Approximately 100 subjects receiving three doses of the AS01E-adjuvanted GSK Biologicals' NTHi-Mcat investigational vaccine containing 10 µg of PD, 10 µg of PE-PilA, and 3.3 µg of UspA2 at Visit 1 (Day 1), Visit 3 (Day 61) and Visit 5 (Day 181) and one dose of placebo at Visit 7 (Day 361).
- **Schedule 2** : Approximately 100 subjects receiving three doses of the AS01E-adjuvanted GSK Biologicals' NTHi-Mcat investigational vaccine containing 10 µg of PD, 10 µg of PE-PilA, and 3.3 µg of UspA2 at Visit 1 (Day 1), Visit 3 (Day 61) and Visit 7 (Day 361) and one dose of placebo at Visit 5 (Day 181).

**Table 1 Study groups and epochs foreseen in the study**

Study groups	Number of subjects	Age (Min/Max)	Epochs	
			Epoch 001	Epoch 002
Schedule 1	100	40 – 80 years	x	x
Schedule 2	100	40 – 80 years	x	x

**Table 2 Study groups and treatment foreseen in the study**

Treatment name	Vaccine/Product name	Study Groups	
		Schedule 1	Schedule 2
10-10-3/AS01E	NTHi-Mcat 10-10-3	x	x
	AS01E	x	x
Placebo	Formulation buffer S9b	x	x

**Vaccination schedule:** at Visit 1 (Day 1), Visit 3 (Day 61), Visit 5 (Day 181) and Visit 7 (Day 361).

**Treatment allocation:** subjects will be allocated to a study group using a centralised randomisation system on internet (SBIR).

**Blinding:** observer-blind (Epoch 001) and open (Epoch 002).

**Table 3 Blinding of study epochs**

Study Epochs	Blinding
Epoch 001	observer-blind
Epoch 002	open

**Sampling schedule:**

- Blood samples for assessment of humoral immunogenicity will be collected from all subjects at Visit 1 (Day 1), Visit 4 (Day 91), Visit 5 (Day 181), Visit 6 (Day 211), Visit 7 (Day 361), Visit 8 (Day 391), Visit 9 (Day 541) and Visit 10 (Day 721).
- Blood samples for assessment of cell-mediated immunogenicity (CMI) will be collected from all subjects in the CMI sub-cohort at Visit 1 (Day 1), Visit 4 (Day 91), Visit 5 (Day 181), Visit 6 (Day 211), Visit 7 (Day 361) and Visit 8 (Day 391).

**CONFIDENTIAL**207759 (NTHI MCAT-008)  
Statistical Analysis Plan Amendment 1 Final

**Type of study:** self-contained.

**Data collection:** Electronic Case Report Form (eCRF), Diary Cards and Phone contacts.

**Safety monitoring:** on going safety evaluations will be performed by the Safety Review Team (SRT) (blinded). Refer to Section 8.10 of the protocol for description of safety monitoring.

### **3. OBJECTIVES**

#### **3.1. Primary objective**

- To evaluate the safety and reactogenicity profile of the NTHi-Mcat vaccine administered according to two vaccination schedules

Refer to Section 4.1 for the definition of the primary endpoints.

#### **3.2. Secondary objectives**

- To evaluate the long term safety profile.
- To evaluate the humoral immunogenicity of the NTHi-Mcat investigational vaccine.
- To evaluate the cellular immunogenicity (CD4+ T cell response) of the NTHi-Mcat investigational vaccine.

Refer to Section 4.2 for the definition of the secondary endpoints.

#### **3.3. Tertiary objectives**

- To explore the T helper profile to the PD-, PE-, PilA-, UspA2 -specific CD4+/ CD8+ T cell responses.
- To evaluate the cellular immunogenicity (CD8+ T cell response) of the NTHi-Mcat investigational vaccine.
- To collect blood samples for assay development/validation and/or for additional evaluation of the immune responses to the investigational vaccine and to other potential pathogens involved in AECOPD.

### **4. ENDPOINTS**

#### **4.1. Primary endpoints**

##### **Safety**

Solicited local and general symptoms.

- Occurrence of each solicited local and general symptom (any and Grade 3) reported within 7 days (Day 1 – Day 7) after each vaccination, within each vaccination schedule.

**CONFIDENTIAL**207759 (NTHI MCAT-008)  
Statistical Analysis Plan Amendment 1 Final

Unsolicited adverse events.

- Occurrence of each unsolicited AE reported within 30 days (Day 1 – Day 30) after any vaccination, according to the Medical Dictionary for Regulatory Activities (MedDRA) classification, within each vaccination schedule.

Serious adverse events.

- Occurrence of any serious adverse events reported from Day 1 (Visit 1) up to and including Day 541 (Visit 9), within each vaccination schedule.

Potential immune-mediated diseases (pIMDs).

- Occurrence of pIMDs reported from Day 1 (Visit 1) up to and including Day 541 (Visit 9), within each vaccination schedule.

## **4.2. Secondary endpoints**

### **Long Term Safety**

Serious adverse events.

- Occurrence of any serious adverse events reported from Day 541 (Visit 9) up to and including Day 721 (Visit 10), within each vaccination schedule.

Potential immune-mediated diseases (pIMDs).

- Occurrence of pIMDs reported from Day 541 (Visit 9) up to and including Day 721 (Visit 10), within each vaccination schedule.

### **Humoral Immunogenicity**

Anti-PD, anti-PE, anti-PilA and anti-UspA2 antibody concentrations, as measured by ELISA, at Day 1, Day 91, Day 181, Day 211, Day 361, Day 391, Day 541 and Day 721, within each vaccination schedule.

Anti-PD, anti-PE, anti-PilA and anti-UspA2 seropositivity, as measured by ELISA, at Day 1, Day 91, Day 181, Day 211, Day 361, Day 391, Day 541 and Day 721, within each vaccination schedule.

Refer to Section [6.4.2.1](#) for the definition of seropositivity.

### **Cellular Immunogenicity on CD4+ T cells**

NTHi-specific and Mcat-specific cell-mediated immune responses as measured by flow cytometry ICS [frequency of specific CD4+ T-cells expressing two or more markers, such as interleukin (IL)-2, IL-13, IL-17, interferon gamma (IFN- $\gamma$ ), tumour necrosis factor alpha (TNF- $\alpha$ ), and CD40 ligand (CD40L)], at Day 1, Day 91, Day 181, Day 211, Day 361 and Day 391, in a sub-cohort of subjects and within each vaccination schedule.

**CONFIDENTIAL**207759 (NTHI MCAT-008)  
Statistical Analysis Plan Amendment 1 Final**4.3. Tertiary endpoints****T Helper profile**

T helper profile of the specific CD4+ and CD8+ T cell response based on the expression of T helper 1, T helper 2 and T helper 17 specific markers at Day 1, Day 91, Day 181, Day 211, Day 361 and Day 391, within each vaccination schedule.

**Cellular Immunogenicity on CD8+ T cells**

NTHi-specific and Mcat-specific cell-mediated immune responses as measured by flow cytometry ICS [frequency of specific CD8+ T-cells expressing two or more markers, such as interleukin (IL)-2, IL-13, IL-17, interferon gamma (IFN- $\gamma$ ), tumour necrosis factor alpha (TNF- $\alpha$ ), and CD40 ligand (CD40L)], at Day 1, Day 91, Day 181, Day 211, Day 361 and Day 391, in a sub-cohort of subjects and within each vaccination schedule.

**5. ANALYSIS SETS****5.1. Definition**

The following analysis sets are defined and will be evaluated at the end of the study:

**5.1.1. Exposed set**

The exposed set (ES) will include all subjects with at least 1 study vaccine administration documented, with respect to the vaccine actually administered:

- A safety analysis will be based on the Exposed, Solicited and Unsolicited Sets:
  - Solicited Set will include all subjects in the exposed set that provided solicited safety data;
  - Unsolicited Set will include all subjects in the exposed set that reported having/not having unsolicited AEs.

**5.1.2. Full Analysis Set**

The full analysis set (FAS) will include all subjects with at least 1 study vaccine administration for whom immunogenicity data are available:

- An **immunogenicity** analysis based on the FAS will include all vaccinated subjects for whom immunogenicity data are available.

The FAS analysis will be performed per treatment as planned in the randomization.

**CONFIDENTIAL**207759 (NTHI MCAT-008)  
Statistical Analysis Plan Amendment 1 Final**5.1.3. Per-protocol set for analysis of immunogenicity**

The per-protocol set (PPS) for immunogenicity will include all subjects in the FAS:

- Who met all eligibility criteria.
- For whom the administration of the vaccines was according to protocol.
- Who complied with the vaccination schedule, as specified in Table 6 of the protocol.
- Who received the study vaccines according to protocol procedures.
- Who did not receive a concomitant medication/ product leading to elimination from the PPS analysis (see section 6.6.2 of the protocol) up to 1 month post-Dose 4 visit (Day 391).
- Who did not present an intercurrent medical condition leading to elimination from the PPS analysis for immunogenicity (see section 6.7 of the protocol) up to the 1 month post-Dose 4 visit (Day 391).
- Who complied with the blood sample timings as specified in table 6 of the protocol.
- For whom post-vaccination immunogenicity results are available for at least 1 assay

Note: subjects for whom pre-vaccination immunogenicity results are not available will only be included in the seropositivity analysis.

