**6.4. Immunogenicity****6.4.1. Analysis of immunogenicity planned in the protocol**

The analysis will be performed on the PPS at first line. If the percentage of vaccinated subjects with serological results excluded from the PPS is more than 10%, a second line analysis will be performed on the FAS.

The CMI analysis will be performed on the FAS – CMI Subset.

**CONFIDENTIAL**207759 (NTHI MCAT-008)  
Statistical Analysis Plan Amendment 1 Final**6.4.1.1. Humoral Immunogenicity****6.4.1.1.1. Within groups assessment****ELISA**

For each group, eight timepoints (Day 1, Day 91, Day 181, Day 211, Day 361, Day 391, Day 541 and Day 721, when blood samples are collected) are considered for humoral immune response against the four antigens PD, PE, PilA and UspA2, for which the following will be computed:

- Seropositivity rate and associated 95% CI at each time point (See Additional considerations for seroresponse definition and assay cut-off values).
- GMCs at each time point and their 95% CIs.

With respect to antibody levels at Day 1 (before 1st dose):

- GMRs at each time point and their 95% CIs.
- Percentage of subjects with 2-fold, 4-fold and 8-fold increase at each time point and associated 95% CI.

With respect to antibody levels at Day 181 (before 3rd dose):

- GMRs at Day 211, Day 361, Day 391, Day 541 and Day 721 and their 95% CIs.
- Percentage of subjects with 2-fold, 4-fold and 8-fold increase at Day 211, Day 361, Day 391, Day 541 and Day 721 and associated 95% CI.

With respect to antibody levels at Day 361 (before 4th dose):

- GMRs at Day 391, Day 541 and Day 721 and their 95% CIs.
- Percentage of subjects with 2-fold, 4-fold and 8-fold increase at Day 391, Day 541 and Day 721 and associated 95% CI.

The distribution of antibody concentrations will be displayed using Reverse Cumulative Curves.

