**6.4.2. Additional considerations****6.4.2.1. Humoral Immunogenicity**

- Calculation of the GMCs will be performed by taking the anti-logarithm in base 10 (anti-log10) of the mean of the log10 ELISA concentration.
- Antibody concentrations below the assay cut-off will be given an arbitrary value of half the assay cut-off for the purpose of geometric mean concentration (GMC) calculation.
- A seronegative subject is defined as a subject whose antibody concentration is below the assay cut-off value (i.e. the ELISA lower limit of quantification). Specifically, the assay cut-off values are defined as follows:

*Anti-PD antibodies: 153 EU/mL*

*Anti-PE antibodies: 16 EU/mL*

*Anti-PilA antibodies: 8 EU/mL*

*Anti-UspA2 antibodies: 28 EU/mL*

Assay cut-off and unit might be subject to change during the study (e.g. in case of assay re-optimization, qualification, (re)validation or standardization). In this case, this will be documented in the clinical study report.

- A seropositive subject is defined as a subject whose antibody concentration is greater than or equal to the assay cut-off value (i.e. the ELISA lower limit of quantification).
- For a given subject and analysis of a given immunogenicity measurement, missing or unevaluable measurements will not be replaced.

**CONFIDENTIAL**207759 (NTHI MCAT-008)  
Statistical Analysis Plan Amendment 1 Final

- The percentage of seropositive subjects and associated two-sided 95% Clopper-Pearson [1] confidence intervals (CIs) will be computed by vaccine group at each visit.
- The 95% CIs for the difference between the percentages of seropositive subjects will be computed using Miettinen and Nurminen method [2] which has superior performance characteristics when rates are close to 0 or close to 1 and when compared to those formed from the Wald statistic.
- GMCs for each group and their ratios at each post-exposure timepoint will be calculated by fitting an ANCOVA model including the country, age category (40 - 59 years or 60 - 80 years) and smoking status (current or former smokers) as factors and pre-Dose 1 concentration (as covariate).

The SAS statements that will be used to calculate the adjusted GMC will be similar to:

```
PROC glm;
  BY timepoint antibody;
  CLASS country age smoking_status group;
  MODEL logtiter= log_baseline country age smoking_status group;
  LSMEANS group / tdiff stderr cl pdiff;
RUN;
```

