**11.2.4. Immunogenicity**

- For a given subject and given immunogenicity measurement, missing or non-evaluatable measurements will not be replaced. Therefore, an analysis will exclude subjects with missing or non-evaluatable measurements.
- The Geometric Mean Concentrations (GMC) calculations are performed by taking the anti-log of the mean of the log concentration transformations. Antibody concentration below the cut-off of the assay will be given an arbitrary value of half the cut-off of the assay for the purpose of GMC calculation. Antibody concentration above the assay cut-off (i.e. the ELISA upper limit of quantification) will be given twice the cut-off value.
- A seronegative subject is a subject whose antibody concentration is below the cut-off value of the assay. A seropositive subject is a subject whose antibody concentration is greater than or equal to the cut-off value of the assay.
- All CIs computed will be two-sided 95% CIs.

**CONFIDENTIAL**207759 (NTHI MCAT-008)  
Statistical Analysis Plan Amendment 1 Final**11.2.5. Safety**

Solicited adverse event: with the exception of 60 minutes after vaccination, solicited adverse events are collected via paper-diary and thus no DCF (data clarification form) will apply in case of inconsistency reporting.

For a given subject and the analysis of solicited symptoms within 7 days post-vaccination, missing or non-evaluable measurements will not be replaced. Therefore the analysis of the solicited symptoms based on the Solicited Safety Set will include only vaccinated subjects for doses with documented safety data (i.e., symptom screen completed). More specifically the following rules will be used:

- subjects who documented the absence of a solicited symptom after one dose will be considered not having that symptom after that dose;
- subjects who reported solicited safety data at a visit, but they didn't report any daily measurement for a certain symptom, they will be counted as missing for that symptom at that visit;
- subjects who documented the presence of a solicited symptom and fully or partially recorded daily measurement over the solicited period will be included in the summaries at that dose and classified according to their maximum observed daily recording over the solicited period;
- doses without symptom sheets documented will be excluded;

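### SAP 5.1.3 drops subjects with no pre-vaccination result from outputs that do not use the Day 1 value, including the Day 181- and Day 361-referenced rises

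*SAP*

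**What the plan says.** SAP Amendment 1, section 5.1.3, admits to the per-protocol set (PPS) subjects who meet the compliance criteria and have a post-vaccination result for at least one assay. It then adds: "Note: subjects for whom pre-vaccination immunogenicity results are not available will only be included in the seropositivity analysis".

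SAP 6.4.1.1.1 plans these humoral outputs for each antigen and group: seropositivity, GMCs, reverse cumulative curves, and GMRs with 2-, 4- and 8-fold rises against three separate references (Day 1, Day 181 and Day 361). The Day 181 block, for example, asks for "GMRs at Day 211, Day 361, Day 391, Day 541 and Day 721 and their 95% CIs".

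SAP 6.4.2.1 describes GMCs in two ways. One is a plain geometric mean: "Calculation of the GMCs will be performed by taking the anti-logarithm in base 10" of the mean log10 concentration. The other is model-based: "GMCs for each group and their ratios at each post-exposure timepoint will be calculated by fitting an ANCOVA model including the country, age category", with the pre-Dose 1 concentration as covariate. The model statement is "MODEL logtiter= log_baseline country age smoking_status group". For the Day 181 and Day 361 GMRs, the same section uses an ANOVA on the log ratio in which the reference concentration is the Day 181 or Day 361 value.

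SAP 11.2.4 gives the general rule. Missing measurements are not replaced, and "Therefore, an analysis will exclude subjects with missing or non-evaluatable measurements".

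**The concern.** The note makes one missing sample decide whether a subject contributes to outputs that do not use it. A subject with valid Day 181 and Day 211 results (Schedule 1), or valid Day 361 and Day 391 results (Schedule 2), carries full information on the rise across the third vaccine dose. The note still removes that subject from the estimate.

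Those rises are the planned outputs closest to the humoral question in Protocol 10.4, which describes the response after the third dose as an increase over the second dose, not over Day 1.

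The full analysis set (FAS) carries no such note, but it is not a dependable safeguard. SAP 6.4.1 analyses it only if more than 10% of vaccinated subjects with serology are excluded from the PPS. Subjects covered by the note appear to remain PPS members, so they may not count towards that trigger.

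**Working it through.** **Step 1. Which outputs need the Day 1 value** (SAP 6.4.1.1.1 and 6.4.2.1)

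| Output | Values it uses | Day 1 needed? |
|---|---|---|
| Seropositivity at a visit | that visit | no (kept by the note) |
| Reverse cumulative curve | that visit | no |
| Unadjusted GMC (antilog of mean log10) | that visit | no |
| GMR and fold rises against Day 181 | visit and Day 181 | no |
| GMR and fold rises against Day 361 | visit and Day 361 | no |
| ANCOVA GMC and GMC ratio | visit and pre-Dose 1 covariate | yes |
| GMR and fold rises against Day 1 | visit and Day 1 | yes |

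The note and the SAP 11.2.4 rule differ in rows 2 to 5. They agree in rows 1, 6 and 7.

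**Step 2. Data-use check.** In 180 simulated subjects, 10 had Day 1 set to missing, and complete-case calculations were run with group as the only factor. The Day 211 geometric mean used 180 subjects, the Day 211/Day 181 model used 180, and the Day 211 ANCOVA used 170. The ANCOVA drops the 10 subjects with or without the note. The other two calculations do not.

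**Step 3. Reproduce the planning figure** (Protocol 10.4: N = 90 evaluable, difference 0.256, SD 0.83, one-sided alpha 0.05, power 90%).

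Power = Φ(0.256 × √90 / 0.83 − 1.645) = Φ(2.926 − 1.645) = Φ(1.281) = 0.900. The noncentral t gives 0.896. The stated 90% reproduces, and 90/(1 − 0.10) = 100 per group.

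**Step 4. Size of the loss.** The documents give no rate of missing Day 1 results, so the rates below are assumed.

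Interval width scales as 1/√n:
- 1% lost: √(1/0.99) = 1.005, or 0.5% wider.
- 5% lost: √(1/0.95) = 1.026, or 2.6% wider.

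Power with m subjects removed from 90, using the Step 3 formula:

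| m | n | Power (normal) | Power (t) |
|---|---|---|---|
| 0 | 90 | 90.0% | 89.6% |
| 1 | 89 | 89.7% | 89.3% |
| 2 | 88 | 89.4% | 89.0% |
| 5 | 85 | 88.5% | 88.0% |
| 9 | 81 | 87.1% | 86.6% |

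From m = 0 to m = 5 the loss is (90.0 − 88.5)/5 = 0.3 percentage points per subject.

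**The case against.** Several points can be made for leaving the note alone.

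- **GMCs.** A reader might infer that the note discards these subjects from every GMC. The documents do not support that. Post-exposure group GMCs and their ratios come from the ANCOVA, which cannot use a subject without the covariate. The within-group line "GMCs at each time point and their 95% CIs" and the geometric-mean definition suggest a descriptive table as well, but the SAP never calls a GMC unadjusted. The GMC loss therefore exists only if such a table is produced. This objection stands.
- **Protocol conflict.** A reader might also infer that the note contradicts Protocol 10.5.3, which contains no such sentence. That is arguable. Its blood-sampling criterion points to Table 10, which lists Visit 1, so a subject with no Day 1 sample could be read as leaving the PPS altogether. On that reading the note is the more lenient rule. The same cannot be said of a sample drawn on time that yields no usable result for one antigen.
- **General versus specific rule.** SAP 11.2.4 is general, and a specific rule can sit beside it. This is fair: the note is stricter than 11.2.4 and does not strictly contradict it. But the SAP gives no reason for the extra strictness.
- **Common population.** Restricting quantitative outputs to subjects with a baseline is a defensible choice. If that was the intention, it should be stated with its rationale.
- **Few cases and no formal test.** Protocol Table 5 and section 5.6.14.1 require blood before vaccination at Visit 1, so few results should be missing. Protocol 10.10 plans estimation, and Protocol 10.4 names no reference visit for the increase over the second dose. Both points limit the weight of the power figures.

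**Conclusion.** The point holds in a limited form. The note needlessly removes subjects from the Day 181- and Day 361-referenced GMRs and fold rises, from the reverse cumulative curves, and from any unadjusted GMC. It costs nothing for the ANCOVA outputs or the Day 1-referenced rises.

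This is a minor, easily corrected flaw and does not threaten the trial's conclusions. With 1–5% of Day 1 results missing, the affected intervals widen by about 0.5–2.6%. The planning power falls by about 0.3 points per subject lost from 90.

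These sizes rest on three assumptions: the unstated missing rate; pre-vaccination meaning Day 1; and, for power, treating the third-dose rise against its pre-dose sample as the contrast behind Protocol 10.4. The second assumption is the natural reading. However, Protocol Table 10 also labels the Day 181 and Day 361 samples as pre-vaccination (before the third and fourth injections), so the term needs defining in any case.

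**What to change.** Replace the note in SAP 5.1.3 with:

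> Subjects without a Day 1 (pre-Dose 1) result for an antigen are excluded, for that antigen, only from analyses that use the Day 1 value (ANCOVA-adjusted GMCs and GMC ratios, Day 1-referenced GMRs and fold increases). They are kept in seropositivity, reverse cumulative curves, any unadjusted GMC, and the Day 181- and Day 361-referenced analyses.

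This also settles what pre-vaccination means and makes the rule antigen-specific. The cost is one sentence. No new programming is needed, because the models already drop records with a missing covariate or reference value. The drawback is that N will differ slightly between the Day 1-dependent tables and the others, so each table should show its own N.
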